1.5 ETHICAL CONSIDERATIONS

This protocol is a combination of planned actions related to routine clinical management of patients, audit, service development, education and clinical research. As such, there is a range of ethical considerations, which overlap these various activities.

Some aspects of the protocol are outside the jurisdiction of GafREC 2.0 but are included in the formal ethics application for completeness.

The protocol (and sub-protocols and linked studies) will be conducted in accordance with the principles of the Declaration of Helsinki 1996 (Recommendations guiding Biomedical Research Involving Human Subjects).

This protocol will be conducted in accordance with the requirements of the UK Data Protection Act 2018 and UK GDPR. The GDPR requires that a Data Protection Impact Assessment (DPIA) be performed for all high-risk processing and, for each DPIA, the advice of the Barts Health NHS Trust Data Protection Officer (DPO) be sought. The processing of participant healthcare data requires a lawful basis under each of Article 6 and Article 9 of the GDPR. Consent as defined in this document is considered “ethical consent” from a governance perspective and may/may not necessarily be a lawful basis for a specific set of data processing operations. The Barts BioResource DPIAs specify the appropriate lawful bases applicable to specific data processing operations and are subject to DPO review and advice and, consequently, are not specified in this Protocol. The Barts BioResource Core DPIA covers most overarching processing operations and is publicly available on the Barts BioResource website.

Data will only be collected and utilised for projects which have ethical, scientific and information governance endorsement. All data will be protected within the requirements of the Barts Health NHS Trust and Connecting for Health.

The protocol will be conducted in accordance with the regulations relating to the Human Tissue Act 2004 and relevant institutional standards of conduct relating to Human Tissue. The residual clinical biological samples to be retained are a by-product of the planned clinical procedures and would otherwise be discarded and incinerated. The prospective collections of up to 50ml of venous blood, saliva, throat, buccal and/or nasopharyngeal swabs, urine, faeces and soft/solid tissue tissue, have minimal ethical concerns or issues.

Follow up and contact tracing are routine activities for clinical care within the NHS. However, access to routine medical and other health-related records will be confined to specific members of the research group/clinical care team, but all future patient contact related to potential participation in clinical research will be related to projects which have a specific and project specific Research Ethics approval. Such a system will undoubtedly reduce the incidence of contact with families of deceased patients which is an on-going problem within the NHS, and which causes considerable distress.

The best interests (clinical, physical, mental and personal) of the patient will always take precedence over the conduct and continuance of this and linked protocols.

A communication plan to inform the whole Barts Health Trust community (service users, carers, clinicians and other Trust staff) is planned to be established regarding the existence, potential benefits and proposed uses of the expanded Barts BioResource.

Envisaged stakeholder participation will facilitate regular consultation on the ethical, societal and practical issues of the project.

1.5.1. PATIENTS COMPETENT TO CONSENT

All competent patients will be clearly informed that their consent will be **optional**.

Specific ethical considerations:

- The patient informed consent is voluntary.
- Each component of the consent is optional.
- Patients will be free to withdraw at any time and without giving a reason.
- Their non-participation or dropping out of the study will not affect their planned or future treatment and care in any way.
- The consent for the Barts BioResource does not affect or influence their rights to decline future approaches or contacts related to participation in clinical research.
- Significant efforts will be made to prevent “*intrusive*” approaches to patient volunteers.
- Any re-contact with the patients will be co-ordinated and approved by the Barts BioResource teams.
- If patient donated biological material remains in an accessible and identifiable form they can request that it is destroyed should they wish. However, should it have been processed into a de-identified form, the

research custodians will not have the capacity or resources to enable destruction.

- Further, should patient biological material, images or data be processed and analysed within a cohort of patients for education, audit, service development or research purposes then the research custodians will not have the capacity or resources to enable destruction or removal from the summated data.
- Should the Barts BioResource identify any clinically relevant findings we will inform patients according to our duty of care. However, analysis of biological samples and tissue may occur with a significant time delay from consenting.

1.5.2 PATIENTS INCOMPETENT TO CONSENT

Generally, and with reference to the Covid-19 pandemic, Barts Health NHS Trust manage a number of patients who are intubated on ventilators and therein lack capacity.

This is especially relevant to patients in the London NHS Nightingale hospital. It is in the national interest, and also potentially in the interest of the patient's welfare, that their clinical information and biological samples are collected and made available to research teams.

This section of the protocol seeks to recruit any patients lacking capacity (including but not limited to such as those on ventilators, severe trauma, cardiogenic shock and similar) to the BBR programme. The following are the required considerations to achieve this in an ethical and legal framework:

Some patients may have an Advanced Directive in place, if this is established in a timely manner then we will conduct their care and potential BBR participation in accordance with their wishes.

We acknowledge the HRA guidance on research without consent, that it can be justified if the gravity of the rights infringement is minor and outweighed by the expected social value of the research and obtaining consent is impractical. We propose that this test is clearly met with reference to:

<http://www.hra-decisiontools.org.uk/consent/principles-ALC-EnglandandWales.html>

We further note and refer to the Medical Research Council's guidance of the **Key principles when considering the participation of adults who lack capacity in research**:

- *The interests of the individual must always outweigh those of science and society.*

- *The research must relate to a condition or impairment that affects the individual or the treatment of this condition.*
- *It must not be possible to conduct equally effective research with adults who have the capacity to consent.*
- *The potential benefits of the project should outweigh the risks: the level of acceptable risk depends partly on the possible benefit to the individual.*
- *Views of those close to the participant should always be sought, unless this is not possible due to particular circumstances.*
- *A participant who lacks capacity should only be included in a study when*
- *there are no indications that he or she objects to this.*

Wherever possible, Next-of-Kin will be consulted in relation to their understanding of the wishes and intentions of the patient, this will be supplemented with the opinion of the nominated clinician (Consultee) not involved in any BBR research present or in future on the data/samples.

As Next-of-Kin [NOK] will generally not be physically present during the current pandemic, the pathway will be by a nominated clinician (Consultee) not involved in any BBR research present or in future on the data/samples; followed by informing the NOK (their wishes to be observed) as soon as is reasonable practicable and appropriate, and finally informed written consent with the patient should they hopefully recover.

The Consultees are not asked to give consent on behalf of the adult, but rather to provide an opinion on the views and feelings of the potential participant. Further, the consultee will be

[a] Told that they are being asked to advise on the views and feelings they believe the adult would have towards participation in the BBR study.

[b] Told that they are free to decide whether they wish to provide this advice or not and

[c] Given sufficient information, in an understandable form, about the BBR study to ensure that they provide you with informed advice.

To this end, we are working directly with the Safeguarding Leads at each individual hospital site to ensure compliance and transparency of the BBR activities and clearly document such activities.

The BBR will develop a robust, transparent and auditable withdrawal system prior to recruitment of these patients and will regularly review such.

Further, we note the principles, provisions and requirements of the Mental Capacity Act 2005 and our teams are experienced in this area.

Risk Analysis: The participation of any patient in the BBR does not convey any significant risk of physical or mental harm. The BBR seeks to collect clinical data and

biological materials such as blood, urine, saliva, swabs and residual samples from clinically relevant procedures.

The application of this amendment will be continuously reviewed by Barts Health NHS Trust governance systems.

2.0 STUDY OBJECTIVES AND DESIGN

2.1 STUDY OBJECTIVES

The Barts BioResource objective is to establish a database of patients who consent to registry participation and the donation of blood, saliva, throat, buccal and/or nasopharyngeal swabs, urine, faeces and soft/solid tissue samples for the purpose of developing a bio repository of donated samples, which will be used for health and related disease based research opportunities. Research opportunities will translate into improving health care. The Barts BioResource aligns with the strategic aims of the NIHR Barts Biomedical Research Centre and its associated delivery organisations.

The now completed pilot phase (approximately 3 months) tested the feasibility and scalability to achieve the extended or main phase's objectives. Specific aims included, but were not limited to assessing recruitment rates, percentage of patients agreeing to enrolment, determining durations of consenting, development and validation of the PowerTrials™ management system, taking of blood samples, processing of blood samples, testing logistics around blood sample transportation to sample storage sites, test of retrieving blood samples from storage sites.

To date the current BBR has recruited >23,400 cardiovascular patients at a primary recruitment rate in excess of 80% approval. Approximately 50 patients have withdrawn their consent. Further, approximately 2,500 patients have been re-consented illustrating an ongoing commitment to inform and retain patient participation (this is recorded as 100% wishing to re-affirm their informed consent). Finally, during this time we have encountered 5 complaints, each of which was resolved transparently and with patient engagement.

2.2 STUDY DESIGN

PILOT: Patients referred for a CMR scan were recruited for the registry due to the elective nature of scans which will facilitate the successful piloting. Also, only a small group of patients (about 5%) who have been scheduled to undergo a CMR scan without contrast agents would need a venepuncture to draw the blood sample. In all other patients the blood sample can be drawn from the intravenous cannula placed for the purpose of administering CMR contrast agent. The pilot phase focused initially on the consenting process, then add the taking of blood samples with necessary processing of blood samples and shipping of blood samples. As anticipated the objectives of the pilot phase were achieved and completed within 3 months and allowed a smooth transition to the extended study guided by the Operational Group.

PILOT AND EXTENDED STUDY:

Prospective, longitudinal cohort study as part of routine clinical care of all patients clinically referred to clinical services within Barts Health NHS Trust. Cross-sectional data will be analysed for prevalence, associations of imaging biomarkers and demographics, clinical findings and blood biomarkers. The long-term follow-up of our patients will allow assessment of the prognostic value of biomarkers.

3.0 SUBJECT SELECTION

Patients will be recruited by attending clinical research staff (at the time of formal consent to Investigation **or** Treatment at The Barts Health NHS Trust as approved by a National Research Ethics Service (NRES) approved Research Ethics Committee.

Patients with capacity will be provided with a full explanation of the nature, purpose and requirements of the study including a concise Information Sheet.

In relation to patients who are incapacitated at their time of recruitment, their Next of Kin (NOK) will be provided with a full explanation of the nature, purpose and requirements of the study including a concise Information Sheet at the earliest suitable opportunity. Further, the process of the Consultee will be fully described and explored with them.

3.1 NUMBER OF SUBJECTS AND SUBJECT SELECTION

PILOT:

We estimated to enrol 600-1000 patients during the 3-month pilot period in our CMR unit. This was mainly the consent for data access and re-contact in the future and only a small proportion of patients were asked to donate a blood sample at this stage, solely for feasibility purposes and not driven by scientific rationale, which will be the case for the extended study.

EXTENDED STUDY:

The proportion of patients enrolled annually will depend on available resources, consent rates and other factors.

The Barts **BioResource** is unique in many aspects, most importantly the ethnic representation, e.g. in our acute coronary artery disease patients with 58% Caucasians, 12% Bangladeshi, 8% Indian, 7% Pakistani, 7% other Asian, 1.5% Black British, 1.5% Caribbean and 5% others.

This ethnic representation will allow scientifically appropriate extrapolation of our findings world-wide.

Human and financial resources available will guide the total number recruited per year. The operational group will advise on which pathways will be prioritised based on scientific merit, feasibility and resources available.

3.2 INCLUSION CRITERIA

The set of criteria that determines that the patient is eligible to participate in the study is:

1. Aged over 18 years.
2. Patients with INCAPACITY will follow the criteria and pathways of Section 1.5.2

OR

3. If Able to understand and voluntarily sign the written Informed Consent Form.
 - a) Agrees specifically access and use of routine medical and other health-related records for:
 - i. Teaching*
 - ii. Audits*
 - iii. Current research and future research*
 - b) Agrees specifically to the donation of human soft and hard tissue.
 - c) Agrees specifically to the additional collections of up to 50ml of venous blood to be collected, processed and retained for research purposes.
 - d) Agrees specifically to the donation of saliva, throat, buccal and/or nasopharyngeal swabs, urine, faeces and soft/solid tissue samples available to be collected, processed and retained for research purposes.
 - e) Agrees specifically to the retention of residual biological tissues and samples that remain after all clinical requirements are completed and the samples related by the relevant pathology lead.

3.3 EXCLUSION CRITERIA

The set of criteria that determines that the patient is ineligible to participate in the study:

1. Any pre-existing requirement of the clinical team to retain or analyse the excised tissue for routine clinical purposes, for example Histopathology.

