Investigator Site: Queen Mary University of London

Signature and Date:

Co- Investigator Name: [name]
Investigator Site: Queen Mary University of London

Signature and Date:

Co- Investigator Name: [name]
Investigator Site: Queen Mary University of London

Signature and Date:

Co- Investigator Name: [name]
Investigator Site: Queen Mary University of London

Signature and Date:

Co- Investigator Name: [name]
Investigator Site: Queen Mary University of London

Signature and Date:

STUDY SUMMARY/SYNOPSIS

TITLE	Barts BioResource
SHORT TITLE	Barts BioResource- BBR
Protocol Version Number and Date	Protocol Barts BioResource Version 11.0; 1st April 2022
Sponsor	Barts Health NHS Trust
Methodology	Establishing, validating and maintaining a clinical and research registry; developing a human tissue bank; collection and analysis of clinical information and non-invasive Monitoring Technology evaluations.
Study Duration	Indefinitely with long-term follow-up via NHS Registries (any kind of health, healthcare and related data available and accessible) and subject to regulatory approvals.
Study Centre	Barts Health NHS Trust
Objectives & Design	
The Barts BioResource resource objective is to establish a database of patients to registry participation and the donation of tissues including blood, saliva, throat, buccal and/or nasopharyngeal swabs, urine, faeces and soft/solid tissue samples for the purpose of developing a bio-repository of donated samples which will be used for clinical health and disease-related research opportunities.
 
Research opportunities are envisaged to translate into improving any aspect(s) of health care.
 
The Barts BioResource aligns with the strategic aims of the NIHR Barts Biomedical Research Centre and its associated delivery partners.
 
The Barts BioResource further supports the NIHR BioResource REC references 17 / EE / 025 and 21 / EE / 0284 in the collection of clinical data and tissue samples.

Number of Subjects/Patients	The long-term vision of the study is to expand as practicable to ALL clinical speciality patients managed by Barts Health NHS Trust, provided sufficient financial and human resources are available.
Main Inclusion Criteria	ALL patients who are referred to and/or managed in the Barts Health NHS Trust are eligible for participation. Being part of other research studies is NOT an exclusion criterion for participation in the BBR and vice versa.

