4.2 SCREENING PROCEDURES

Initial PILOT:

There were no specific screening procedures other than those detailed in the Inclusion/Exclusion criteria.

At the time of clinical appointment, the patients had the nature of the study, the procedures and the risks fully explained both verbally and as part of the PIS (Patient Information Sheet). The patients were invited to sign an optional Informed Consent Form in which they acknowledged that they were willing to be enrolled in the study; that they agreed to provide personal particulars to the investigators and recognise that these may be available to non-medical investigators and may be sighted by the Sponsor.

During the screening evaluation the following procedures will be conducted and recorded for all Patients:

- Informed Consent ([Section 4.1](#); [Section 8.6.3](#))
- Evaluation of compliance with inclusion and exclusion criteria ([Sections 3.2](#) and [3.3](#))

- Access to the result of relevant existing or planned laboratory tests; including clinical imaging, haematology and biochemistry.

Patients who satisfy all of the inclusion and exclusion criteria, who signed the Consent Form, and who agree to the conditions of the study, were eligible to enter the study.

EXTENDED STUDY:

The procedures are the same as described for the pilot study the exception is for Incapacitated patients.

Generally, and with reference to the COVID19 pandemic, Barts Health NHS Trust have a number of patients who are intubated on ventilators or for other clinical management, and therein lack capacity.

This is specifically relevant to all patients in the NHS Nightingale hospital and in the Barts Health NHS Trust Intensive Care Units. It is in the National Interest, and also potentially in the interest of the patient's welfare, that their clinical information and biological samples are collected and made available to research teams.

This section of the protocol seeks to recruit patients lacking capacity (such as those on ventilators, severe trauma, cardiogenic shock and similar) to the BBR programme. The following are the required considerations to achieve this in an ethical and legal framework:

Some patients may have an Advanced Directive in place, if this is established in a timely manner then we will conduct their care and potential BBR participation in accordance with their wishes.

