4.4 SCHEDULE OF TREATMENT FOR EACH VISIT

Initial PILOT:

Current clinical practice:

All patients referred for CMR scans were sent information sheets explaining the scan procedure and a questionnaire asking questions relevant to safety using MRI.

On the day of the appointment, they were seen by a clinician/ radiographer authorised for MRI and the 'Safety Questionnaire' verified for eligibility to MRI scanning, administration of gadolinium contrast and in cases of perfusion imaging to adenosine, a pharmacological stressor agent.

Almost all patients (95%) needed one intravenous cannula inserted to enable delivery of contrast ± stressor agent during the scan. The current scan time varied from 30 to 45 minutes depending upon the clinical question and thus the type of image sequences performed.

Subsequent Approved changes:

All competent patients will continue to receive information as before with the addition of the information sheet inviting participation for the any of each of the following:

- Opportunity to (re-) review the patient information sheet and to meet the research nurse to have any remaining related questions answered (up to 15 mins)
- Consenting to this research study (3-5 mins)
- Blood sampling (in majority of the cases via the intravenous cannula as is clinical practice, thus in almost all cases no additional needle insertion necessary, 3-5 mins)

It is always highlighted that their participation is solely voluntary for each of the above (may consent to participate in one or more) and by no means will it affect their proposed clinical management.

This section applies to **both the Initial Pilot and the Extended study protocol:**

- No additional visits or treatments are required by this protocol.
- Patients who agree to donations of up to 50ml venous blood sample(s) per occasion will have the blood collected at the time of routine clinical venepuncture. An additional venepuncture will be necessary if no clinical venepuncture is scheduled to be performed on the patient attendance.
- The donation of saliva, throat, buccal and/or nasopharyngeal swabs, urine, faeces and soft/solid tissue samples that will be collected, processed and retained are for research purposes as defined by the BBR protocol.
- Consented patients who are undergoing surgery will have tissue samples harvested by the appropriate clinical professional.

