5.2 SAMPLE COLLECTION/LABELLING/LOGGING

Collection of Blood Samples

Barts BioResource personnel will follow detailed Standard Operating Procedures for processing, logging and storage of samples, including adverse event standard procedure and reporting. A blood sample (up to 50 ml) will be obtained from all consented individuals by a nurse/ technician trained in cannulation and venepuncture. A summary of the blood processing procedure is provided in Figure 2 below.

Up to 50mls of blood will be collected into aliquots. These will include 2x 4.5ml EDTA, 1x 5ml PST, 2x 5.0ml STT/gel, up to 2x 2.5ml PAXgene for RNA and a 20 ml “floating” sample. The floating sample will be available and processed for specific projects in accord with access applications approved by the Barts Heart Centre peer review committee. Blood will undergo on-site processing and samples will be aliquoted into bar coded cryovials as follows: EDTA (plasma) to 9 cryovials, EDTA (white cells) to 2 cryovials, LH (PST) up to 4 cryovials, SST up to 8 cryovials, PAXgene RNA to up to 10 cryovials (Figure 2).

Each cryovial will be individually logged into the Barts [BioResource](#) database (LIMS) by research staff using a bar-code reader and then stored in a secure location on-site in an appropriate freezer aligned to the appropriate management of the samples obtained (e.g. -20°C, -40°C or -80°C freezers). Samples will be collected on an approximately monthly basis by secure courier and transported on dry ice for long term storage with a 3rd party supplier where they will be stored at an appropriate temperature until they are retrieved for analysis, which may be up to 20 years after sampling.

Samples will be stored with the National Biosample Centre (‘biocentre’) under contract with the Sponsor and/or its delivery partners to access the logistical requirements before a long-term solution is confirmed (Figure 3).

Residual tissue will be collected on a case-by-case basis according to routine pathology practice.

[figure not shown]

Figure 1: Summary of an Example Standard Operating Procedure (SOP) for Business As Usual processing and on-site short term storage of research biological samples (blood, saliva, throat, buccal and/or nasopharyngeal swabs, urine, faeces, soft/hard tissues and any other biological samples available).

[figure not shown]

Figure 2: Summary of logistics pathway for sample storage and transfer.

Labelling of all study biological materials:

- Subject Number

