5.5 SAMPLE ANALYSIS PROCEDURES

This protocol was led by a number of key principles. The bioresource aims to collect samples allowing the widest possible range of assays that could plausibly be envisaged for the future, and to avoid collection, processing or storage approaches that would inherently preclude such assays (i.e. "future proof" the collection as far as possible given current knowledge and available resources).

Sample Type	Selection Criteria
Blood	
 • Variety of fractions: plasma, serum, white cells, red cells, peripheral blood lymphocytes • Wide range of biomolecules: DNA, RNA [5' ends], proteins, analytes • Wide physiological coverage: genome, proteome and metabolome, haematological parameters • Suitable for a very wide range of assay technology • Ease and low cost of collection
Saliva, throat, buccal and/or nasopharyngeal swabs	
 • Wide range of biomolecules: DNA, RNA, proteins, lipids • Wide physiological coverage: genome, proteome • Suitable for microbial/fungal/viral species detection, biomarkers • Suitable for a wide range of assay technology • Ease and low cost of collection
Urine and faeces	
 • Range of biomolecules: DNA, protein • Physiological coverage: metabolomics, biomarkers, hormones, ions • Suitable for a wide range of assay technology • Ease and low cost of collection
Soft/solid tissue samples	
 • Biomolecules: DNA, RNA [5' ends], proteins, analytes • Wide physiological coverage: genome, proteome and metabolome • Suitable for a very wide range of assay technology • Research samples will be collected following clinical biopsy (if performed) and only if minimal risk to patient.

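### Section 3.3 writes a rule about excised tissue as an exclusion of the patient from the whole study, which conflicts with the synopsis and with Sections 1.5.1, 3.2(e) and 5.5

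*Protocol*

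**What the plan says.** Section 3.3 of the protocol opens with "The set of criteria that determines that the patient is ineligible to participate in the study" and lists one item: "Any pre-existing requirement of the clinical team to retain or analyse the excised tissue for routine clinical purposes, for example Histopathology".

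Section 4.2 uses the criteria as the entry gate. Those eligible to enter are "Patients who satisfy all of the inclusion and exclusion criteria, who signed the Consent Form" and who accept the study conditions. That sentence stands under the pilot, but the extended study takes over the same procedures, with an exception only for incapacitated patients.

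Other current text describes a wider population and a tissue collection that follows clinical use:

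- Synopsis, Main Inclusion Criteria: "ALL patients who are referred to and/or managed in the Barts Health NHS Trust are eligible for participation".
- Section 1.5.1: each part of the consent is optional.
- Section 3.2(e): "Agrees specifically to the retention of residual biological tissues and samples that remain after all clinical requirements are completed".
- Section 4.4: "Consented patients who are undergoing surgery will have tissue samples harvested by the appropriate clinical professional".
- Section 5.2: "Residual tissue will be collected on a case-by-case basis according to routine pathology practice".
- Section 5.5, on soft and solid tissue: "Research samples will be collected following clinical biopsy (if performed) and only if minimal risk to patient".

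**The concern.** The item is a condition on a piece of tissue, but the sentence above it turns it into a condition on a person. The BioResource also collects record access, blood, saliva, swabs, urine, faeces, re-contact permission and long-term follow-up. None of these depends on whether a pathologist needs an excised specimen. Nothing in Section 3.3 confines the item to tissue donation.

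Two things are at stake. The first is who enters the cohort. Section 2.2 plans cross-sectional prevalence and association analyses and an assessment of the prognostic value of biomarkers. An exclusion triggered by histopathology depends on the disease a patient has and the procedures undergone, so a cohort filtered by it would differ from the stated population in ways related to those analyses.

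The second is compliance. Under Section 8.6.11, a subject admitted without qualifying under the protocol may be unusable for analysis. Staff who sensibly enrol a biopsied patient for records and blood would, on the literal text, create that problem. Staff who follow the text would turn the patient away.

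**Working it through.** The protocol states no figure on this point, so the check is mainly a comparison of texts.

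**Unit of the rule.** The lead-in to Section 3.3 names the patient and the study. The item names the excised tissue. No qualifying words link the item to the tissue component, and Section 4.2 applies the list to study entry as a whole.

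**Comparison with the other sections.**

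1. *Synopsis.* All Trust patients are eligible. An exclusion may narrow an inclusion statement, so this conflict carries little weight alone.
2. *Section 1.5.1.* With optional components, a patient can join for data or blood and give no tissue. Under the literal Section 3.3, the state of the tissue closes every component. These conflict directly.
3. *Section 3.2(e).* Keeping tissue left after clinical requirements are met presupposes participants whose tissue had such requirements. For excised tissue, those are patients whom Section 3.3 bars.
4. *Section 5.5.* Research sampling after a clinical biopsy presupposes participants who had one. Where the biopsy goes to histopathology, Section 3.3 bars them.
5. *Section 5.2.* Residual tissue obtained through routine pathology practice points the same way as items 3 and 4.
6. *Section 4.4.* Taking tissue from surgical participants is not in itself a conflict, because some surgical tissue has no clinical requirement.

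**Direction of the selection.** Let *p* be a disease's share of the patients approached, *h1* the proportion of them whose tissue must go to pathology, and *h0* that proportion among the other patients. With the exclusion applied literally and all else equal, the disease's share of those enrolled is

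p(1 − h1) / [p(1 − h1) + (1 − p)(1 − h0)].

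This equals *p* when h1 = h0, falls below *p* whenever h1 > h0, and reaches 0 when h1 = 1. The documents give none of *p*, *h1* or *h0*. The direction is therefore clear for a disease diagnosed or treated through excision, but the size could lie anywhere from no change to complete removal.

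**The case against.** The strongest reply is that nobody would read the item at patient level. Reference to excised tissue presupposes an excision from which tissue might be donated, and it means little for someone asked only for records. Section 3.2 cannot be read literally either: items (b) to (e) would then oblige every competent participant to agree to tissue and blood donation, against Section 1.5.1. Both lists may simply work component by component. This is good evidence of intent, and recruitment may already follow it. It does not cure the text, because Section 3.3 contains no such limit and Sections 4.2 and 8.6.11 give the text effect.

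A second reply concerns timing. The item speaks of a pre-existing requirement and Section 3.2(e) of requirements that are completed, so the bar might lift once the tissue is released. Section 3.3 does not say so. Section 3.0 places recruitment at formal consent to investigation or treatment, when the requirement may still be open.

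Third, Appendix 5 describes in general how eligibility checklists are built from protocol criteria. No BioResource checklist is shown, so how the item is applied in practice is unknown. That stands.

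Fourth, resources and pathway priorities already shape enrolment (Sections 1.1 and 3.1), so the registry share of a disease would not equal its source prevalence in any case. That also stands, but a disease-related exclusion within a pathway is a further distortion and an avoidable one.

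A reader might go further and infer that the residual-tissue collection has no eligible donors. The documents do not support this. Excised tissue with no clinical requirement falls outside the item: Section 1.5 describes residual material that would otherwise be discarded, and Section 1.1 gives atrial appendage and pulmonary vein tissue as examples of what is collected. Residual samples that were never excised, such as leftover blood, also fall outside it.

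**Conclusion.** The point holds as a defect of wording with operative effect: a specimen restriction is written as exclusion of the patient from the whole study. It conflicts most clearly with Sections 1.5.1, 3.2(e) and 5.5, and less strongly with the synopsis. Applied literally, it would select on disease and procedure before the analyses in Section 2.2.

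The conclusion assumes only that Section 3.3 is applied as written through Section 4.2. Other sections suggest a specimen-level intent, and the documents do not show which reading is used in recruitment. The number of patients affected cannot be estimated, and any percentage would rest wholly on assumed histopathology rates.

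A reader might also infer that biopsied, operated or cancer patients are in fact being removed, given the histopathology example and the large cancer centre named in the Executive Summary. The documents do not show this. They record no decision to exclude such patients and no counts. The supported statement is that the text, if followed, would exclude those whose excised tissue has a clinical requirement.

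**What to change.** Reconcile Section 3.3 with the synopsis and Sections 1.5.1, 3.2(e), 4.4, 5.2 and 5.5:

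- Remove the item as a participant exclusion and restate it, for example in Sections 4.4 and 5.2, as a rule on the specimen: tissue with a clinical requirement is not taken for the BioResource until the pathology lead releases it, as Section 3.2(e) already implies.
- State that the patient remains eligible for records, blood, other samples, re-contact and follow-up, subject to the consent given for each.
- Align any eligibility checklist built from Sections 3.2 and 3.3.

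The cost is a wording amendment with its usual approval, and a checklist edit if one carries the item. No extra patients, visits or procedures are needed.
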